## **Secondary Outcome Measures**

**Posttraumatic Cognitions Inventory, 9-Item Version (PTCI-9).** The PTCI-9 is a 9-item well-validated self-report measure of maladaptive beliefs that commonly manifest in PTSD (Wells et al., 2019). This measure will be administered at pre-treatment, post-treatment, and the 1-month follow-up, and at the beginning of each session to index change in problematic trauma-related beliefs.

**Mood and Anxiety Symptom Questionnaire (MASQ).** The MASQ is a brief 26-item questionnaire with three separate subscales including general distress, anxious arousal, and anhedonic depression (Casillas & Clark, 2000). This measure will be administered at pre-treatment, post-treatment, and the 1-month follow-up.

**PTSD Safety Behaviors Questionnaire (PSBQ).** The PSBQ is a 10-item validated measure of unnecessary protective actions, including avoidant behaviors, that are common in cases of PTSD, and are widely believed to serve to maintain and exacerbate trauma-related symptoms (Foulser & Telch, 2019). This measure will be administered at pre-treatment, post-treatment, and the 1-month follow-up.

**Emotional Reactivity and Numbing Scale (ERNS).** The ERNS is a 62-item self-report measure that assesses tendencies to experience a restricted range of emotions, or emotional numbing, including in response to emotionally arousing situations (Orsillo, Theodore-Oklota, Luterek, & Plumb, 2007). This instrument will be administered at the pre-treatment assessment visit.

**Sheehan Disability Scale (SDS).** The SDS is a 5-item measure that assesses disability and functional impact associated with symptoms (Leon, Shear, Portera,

& Klerman, 1992). This instrument will be administered at the pre-treatment, post-treatment and 1-month follow-up assessment visits.

**Clinical Global Impressions (CGI).** The CGI is a 5-item, clinician-rated measure that provides a global assessment of severity, functioning, and improvement over the course of treatment (Kadouri, Corruble, & Falissard, 2007). This measure will be administered at the pre-treatment, post-treatment, and 1-month follow-up assessment time-points.

**Columbia-Suicide Severity Rating Scale (C-SSRS).** The C-SSRS is a widely used standard assessment of lifetime and follow-up suicidality, including thoughts of intent, methods, plans, and preparatory efforts, as well as suicidal and self-harm behaviors (Posner et al., 2011). This instrument will be administered at the pre-treatment, post-treatment, and 1-month follow-up time-points.

### **Treatment Process Measures**

**Pre-session Self-Report Measures.** Prior to each session, participants will complete a number of self-report measures, which will be reviewed with the participant at the beginning of each session. The pre-session measures are indicated in **Table 1**, and described in the sections above, and include: the PCL-5, PTCI-9, and PHQ-9.

**Subject Units of Distress Scale (SUDS).** The SUDS is a simple visual analogue scale reflecting anticipated, peak, and/or current distress levels, rated from 0 = “No distress” to 100 = “Extreme distress.” This scale is commonly used as part of standard PE to assess the level of emotional arousal, engagement, and response to in-session and between-session exposure practices (Wolpe, 1973).

**Prolonged Exposure Therapist Questionnaire (PETQ).** Our group developed the PETQ, which is an 8-item Likert-type scale, as a means to capture therapists’ assessments of session-by-session trauma-memory engagement, recovery of significant details, meaning making, and change in trauma-related beliefs. This instrument will be completed by study therapists immediately following each treatment visit that involves imaginal exposure and processing components (i.e., sessions 2-6).

### **Remote Affective and Physiological Measures.**

As implemented in our ongoing VA study (PI: [name]), participants will undergo standardized trauma interview procedures at pre-treatment, post-treatment, and the 1-month follow-up that will be audio and video recorded. This will involve capturing reactivity to (1) 1-min. standardized neutral imagery (e.g., describing and recounting a mundane morning routine); (2) a 5-min. standard trauma interview designed to elicit emotional, cognitive, and sensorial details related to the traumatic event; followed by (3) very brief, 1-min. imaginal “hot-spot” revisiting, in which participants will be guided in verbally recounting and vividly imagining the worst part of their index traumatic event. Additional details regarding these procedures can be found in the appendix (see standard trauma interview form in the appendix). Video and audio streams will be analyzed using open-source software to extract affective and physiological signals based solely on visual and acoustic properties of webcam footage. The specific markers to be extracted are described in the following sections.

**Remote photoplethysmography (rPPG).** We will apply state-of-the-art procedures for extracting high fidelity heart rate data from video (van der Kooij & Naber, 2019) acquired via commercial-grade webcams already in use within our clinic, and comparable to that used nationwide in the delivery of VA telemental health. Video quality will be consistent across assessment sessions (1080p, 60 frames per second). Default settings for video recordings will be used, and any automated corrections (e.g., dynamic adjustments for variations in brightness) will be turned off. Open-source MATLAB-based software (<https://github.com/marnixnaber/rPPG/>) will be used to extract heart rate from video recordings. This will involve a series of automated steps, as described by van der Kooij and Naber (2019), including: (a) spatiotemporal cropping; (b) facial detection and selection of target pixels on the skin surface; (c) averaging/filtering signals based on dynamic color variations; (d) independent component analysis; (e) fast Fourier transformations; (d) power spectra filtering; and (f) corrections for respiration and movement artifacts. Previously validated parameters will be used to extract the final rPPG heart rate, which will be defined as the tallest power peak across components. Heart rate variability will also be calculated, based on the root mean square of successive differences in beat-to-beat intervals (RMSSD). Finally, in addition to heart rate indices, respiratory rate will be similarly derived from the rPPG signal using validated acquisition, processing, and analytic steps, including applying MATLAB-based algorithms for spatiotemporal filtering, motion correction, and signal pruning to produce contactless, high-quality respiratory rate signals (Chen et al., 2019).

**Facial emotion expressivity.** Whereas coding of emotional facial expressions by independent raters is a well-established practice in the affective sciences, advanced algorithms based on artificial intelligence can now be applied to visual signals from video to allow for automatic and continuous detection of emotional facial features, providing a more objective means of measuring expressivity in comparison to subjective and observer-based assessments (Samadiani, Huang, Cai, Luo, Chi, Xiang, & He, 2019). Following a similar approach as with the rPPG data, MATLAB-based algorithms will be applied to the video recordings to extract continuous measures of affective valence, arousal, and intensity, and emotion classification based on empirically-derived facial features associated with each primary emotion (i.e., joy, sadness, fear, anger, and disgust), as well as affective displays associated with physical pain.

**Affective vocal features.** In addition to the metrics above that rely on visual features, affective vocal features will be extracted from auditory streams of the video recordings by applying established acquisition, processing and analytic pipelines, utilizing MATLAB-based scripts to automatically isolate the patient's voice, and subsequently extract and quantify vocal prosodic and spectral features characteristic of emotional states (e.g., Gunawan, Alghifari & Kartiwi, 2018).

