## 10.0 Data Management

**Data Acquisition.** If (and only if) ultimately approved by the VA, we propose the use of VA Qualtrics, which is a secure, FedRAMP-authorized online data capture system that is widely used as a HIPPA-compliant web-based means to collect sensitive research data. Moreover, if approved, in addition to remotely collecting validated self-report questionnaire data from participants using this platform, we also request leveraging Qualtrics' functionality to integrate java script, which would enable us to directly capture audio and visual data from the participant's side from their webcam and microphone. This is an excellent alternative to our initially proposed procedures, which involve collecting streamed, then captured (i.e., on the clinician's side) footage. This is problematic due to significant temporal distortion and low sampling rate for screen-captured footage on currently deployed telehealth platforms approved by the VA (i.e., Teams, Webex, and VVC). As mentioned, the use of Qualtrics will be entirely contingent on obtaining full MUSC IRB and VA R&D approval for our proposed use. If ultimately not approved, we will continue to implement our procedures that involve capturing questionnaire data with hard copies, by mail.

**Data Preparation.** Pre-processing of data as the study progresses will allow for more expedient dissemination of study findings. As appropriate, pre-processing will follow standard best practices to ensure excellent data quality and security. Prior to analyses, data will be visually and statistically inspected for the presence of aberrant data points, which will be omitted prior to analyses.

**Analytical Plan.** Descriptive statistics will be reported for safety, feasibility, tolerability, and acceptability. Linear mixed-effects models will be used to characterize trajectories of change in symptoms and impairment, while controlling for potential confounders, such as baseline severity.

Following standard pre-processing steps, analyses will be conducted using generalized linear models, and will proceed in a bottom-up manner involving selection of the best fitting fixed and random growth terms, followed by adding predictors of interest. Factors (e.g., sex) will be dichotomously coded, whereas all continuous predictors will be scaled and centered as a function of baseline values to allow for meaningful interpretation of effects as indicative of reliable change.

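### Section 9.0 promises uniform 1080p/60 fps video, but Section 10.0 calls platform-captured footage distorted and low-rate, so RMSSD is open to capture error

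*Combined protocol and SAP*

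**What the plan says.** Section 9.0, under remote photoplethysmography, says that "Video quality will be consistent across assessment sessions (1080p, 60 frames per second"), with footage "acquired via commercial-grade webcams already in use within our clinic". No condition is attached. The same paragraph defines two cardiac indices. Heart rate is the value "which will be defined as the tallest power peak across components", and "Heart rate variability will also be calculated, based on the root mean square of successive differences in beat-to-beat intervals (RMSSD").

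Section 6.0 places all outcome assessments on VVC or a comparable approved platform, entirely remotely. Section 9.0 schedules the recorded trauma interview at pre-treatment, post-treatment and 1-month follow-up, in segments of 1, 5 and 1 minutes.

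Section 10.0 (Data Acquisition) describes "our initially proposed procedures, which involve collecting streamed, then captured" on the clinician's side, and calls this problematic because of "significant temporal distortion and low sampling rate for screen-captured footage on currently deployed telehealth platforms approved by the VA". The proposed alternative captures audio and video on the participant's side, but "the use of Qualtrics will be entirely contingent on obtaining full MUSC IRB and VA R&D approval for our proposed use". The fallback reads: "If ultimately not approved, we will continue to implement our procedures that involve capturing questionnaire data with hard copies, by mail". It does not mention video.

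**The concern.** Section 9.0 asserts a property of the recordings that Section 10.0 says the default route lacks, and the remedy is not yet in place. If approval is refused, the plan as written computes RMSSD at three visits from footage it has itself described as unsuitable. If approval comes during the study, the route may change partway through a participant's visits. Even without that, Section 6.0 allows several platforms and does not require the same one each time.

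The design is single-arm and pre-post, so no control group would separate a change in capture from a change in the participant. The physiological indices are outcome-assessment measures at all three visits, and Section 9.0 names CAPS-5 as the criterion against which the objective measures are to be related. The only quality rule before analysis, in Section 10.0, is inspection for and omission of aberrant points. That would not reveal a systematic shift affecting a whole recording.

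**Working it through.** The plan has no figure of its own to reproduce here. The check sets the statements side by side and then asks how large the effect on RMSSD could be.

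**Side by side.** Visits are remote over telehealth platforms (Section 6.0). Footage from those platforms, captured at the clinician's end, has temporal distortion and a low sampling rate (Section 10.0). Footage is consistent at 1080p/60 fps (Section 9.0). The first two statements exclude the third unless participant-side capture is approved and actually delivers that rate. No other section resolves this. The documents contain no minimum frame rate, timestamp check, record of capture route or adjustment for route.

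**Inputs.** From the plan: 60 fps, RMSSD from beat-to-beat intervals, three visits. Assumed, because the plan gives no value: low rates of 30 and 15 fps, a true RMSSD of 20 ms (range 15 to 40 ms), and beats placed at the nearest frame.

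**Formula.** The frame interval is T = 1000/fps ms. Nearest-frame placement gives a uniform error with variance T²/12. RMSSD uses the difference of two successive intervals, t₃ - 2t₂ + t₁, so the added variance is (1 + 4 + 1) × T²/12 = T²/2. Hence observed RMSSD ≈ √(true² + T²/2).

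| fps | T (ms) | T²/2 | floor T/√2 (ms) | reading when true = 20 ms |
|---|---|---|---|---|
| 60 | 16.7 | 138.9 | 11.8 | √538.9 = 23.2 |
| 30 | 33.3 | 555.6 | 23.6 | √955.6 = 30.9 |
| 15 | 66.7 | 2222.2 | 47.1 | √2622.2 = 51.2 |

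Moving from 30 to 60 fps between visits gives 23.2 - 30.9 = -7.7 ms, and -7.7/30.9 = -25%, with no true change. For true values of 15, 25 and 40 ms the shift is -8.9, -6.7 and -4.7 ms. From 15 to 60 fps, with true = 20 ms, it is 23.2 - 51.2 = -28.0 ms. Simulation at 80 bpm with 1- and 5-minute windows agrees: a true 25 ms read about 28, 34 and 53 ms at 60, 30 and 15 fps.

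**Sensitivity to the beat-timing method.** Suppose each beat is instead located by a quadratic fit to a smooth simulated pulse (1-minute windows, true = 20 ms). At 60 and 30 fps the readings are 19.8 and 19.9 ms without noise, 20.1 and 20.7 ms with 2% noise, and 22.6 and 25.2 ms with 5% noise. The gap between 60 and 30 fps is then 0.1 to 2.6 ms. At 15 fps with 5% noise the reading is 35.1 ms.

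**Temporal distortion.** Frame rate is only part of what Section 10.0 describes. An assumed random timing error with SD 20 ms per beat adds 6 × 20² = 2400 to the variance. At 30 fps the reading becomes √(400 + 555.6 + 2400) = 57.9 ms.

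**Heart rate.** The simulated spectral peak stayed at 80 bpm under random jitter, even at 15 fps. It moves only if the assumed frame rate is wrong: footage at 57 fps processed as 60 fps turns 80 into 80 × 60/57 = 84.2 bpm.

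**When a false change arises.** It arises only when capture differs between a participant's own visits. One participant's assessments span roughly 7 weeks: up to 1 week to the first session, a 10-day treatment window, then 1 month. Only those whose visits straddle a switch, or whose platform or achieved rate varies, are exposed. Constant distortion inflates RMSSD at every visit and dilutes change.

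**The case against.** Section 10.0 recognises the problem openly and proposes a sensible remedy. That stands, but the remedy is conditional and the fallback omits video, so the promise in Section 9.0 is still unsupported.

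The illustrated size depends on one implementation. Neither 30 nor 15 fps appears in the documents, and sub-frame interpolation removes most of the difference between 30 and 60 fps. This stands: the 8 ms is one end of a range, not an estimate for this trial.

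A reader might also infer three stronger things that the documents do not support:

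- That RMSSD cannot be obtained because the pipeline keeps only a spectral peak. The tallest-peak definition applies to heart rate alone; RMSSD is defined separately from beat-to-beat intervals. At most, the beat-detection step is not described.
- That any change in physiology between visits could be a capture artefact. Spectral-peak heart rate is biased only by an undetected frame-rate error, and a constant capture route does not create a visit-to-visit shift.
- That the trial's main conclusions are at risk. The physiological indices are not listed under the primary or secondary outcome headings, and no aim or hypothesis in Section 1.0 uses them.

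Local capture is not a guarantee either. It would use the participant's own webcam, whose frame rate is nowhere stated, and the same route need not mean the same rate. The criterion should therefore rest on the achieved rate and timing as well as the route.

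**Conclusion.** The point holds, limited to the physiological indices and chiefly to RMSSD. Section 9.0 states a recording standard that Section 10.0 contradicts for the default route, and nothing in the documents settles which applies.

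Poor capture can inflate RMSSD at every visit, and can create a false change where route or achieved frame rate differs between a participant's visits. For a true RMSSD of 20 ms and a move from 30 to 60 fps, the false change is about -8 ms (-25%) with nearest-frame timing and about 0 to 3 ms with interpolation. A lower starting rate would make it larger, and temporal distortion would add error. These sizes rest on the assumed frame rates, true RMSSD and beat-timing method; the contradiction itself rests on no assumption. It should be corrected, but it does not threaten the safety, feasibility, acceptability or symptom results.

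**What to change.** 1. Reconcile Sections 9.0 and 10.0: make the 1080p/60 fps statement conditional on footage verified to reach it, and state the video route to be used if Qualtrics is not approved.
2. For every recording, log the capture route and the achieved frame rate, with frame timestamps, and use the achieved rate in processing. These may not be recoverable later.
3. Prespecify a frame-rate and timing criterion, and report RMSSD only from recordings that meet it.
4. Make each within-participant comparison of two visits only where both recordings meet the criterion, share the same route and have comparable achieved frame rates. Keep a valid pair even if the third visit fails; with 20 completers planned, requiring all three would discard usable data.

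The cost is a few metadata fields and some analysis wording. The downside is that RMSSD is lost for recordings that fail the criterion, possibly for every participant if only screen capture is available.

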## Treatment Procedures.

**Telehealth-delivered massed imaginal exposure therapy.** Within 1-week of completing the initial pretreatment assessment visit and eligibility determination, enrolled participants will receive a total of six 60-minute treatment sessions, with sessions 2-6 scheduled daily, following the manualized procedures developed for use by Zoellner et al., (2017), as previously implemented by Co-I [name]. This

protocol closely follows core elements of PE, which is a gold standard intervention widely disseminated throughout the VA. In addition to in-session components, participants will also complete between-session assignments involving listening to the entire session recording for session 1, and listening to their imaginal exposures for sessions 2-6. Additionally, the treatment provider will conduct a brief (~5-10 min.) nightly check-in with participants via Doxy.me, VVC-now, or another VA-approved videoconferencing or secure messaging platform. More details regarding in-session components are provided in the following sections.

[figure not shown]
**Session 1** primarily consists of psychoeducation delivered in an interactive (rather than purely didactic) manner to promote understanding of participants' trauma-related reactions, symptoms, and functional impairment. A brief rationale for treatment is also provided in this initial visit to support understanding and engagement with subsequent exposure-based visits.

**Session 2** begins with a more detailed, but still brief rationale for treatment, followed by 30 to 40 min. of imaginal exposure and approximately 15 min. of discussion (i.e., emotional processing) aimed at promoting elaboration on thoughts and feelings associated with participants' index trauma.

**Sessions 3-5** consist of ~30-40 min. of imaginal exposure, and ~15 min. of processing trauma-related thoughts and feelings. As treatment progresses, participants' will be encouraged to focus on "hot-spots", reflecting the most distressing parts of their index trauma.

**Session 6** is the final treatment visit, including 30 min. of imaginal exposure, 15 min. of processing, and 15 min. of reviewing treatment progress, promoting maintenance of treatment gains, discussing treatment termination, and planning follow-up assessments.

The procedural flow is illustrated in **Figure 1** below.

**Figure 1. Study procedures.** Outcome assessments will take place at pre-treatment, and at 1-week, and 1-month after treatment. At each assessment, remote photoplethysmography (rPPG) will be utilized to extract heart rate data from videos of a standard trauma-focused interview administered at pre-treatment, post-treatment, and 1-month follow-up, in addition to other video-based measures of affective reactivity, a clinical diagnostic interview, and self-report measures. Tolerability, acceptance, and perceived utility of the procedures based on the providers' and participants' self-reports will also be collected. Treatment process measures based on patient self-report will be collected before and just after each of 6-daily treatment sessions. Provider ratings of engagement and emotional processing will also be collected immediately following each treatment session that includes imaginal exposure and processing components (i.e., sessions 2-6).

## Participant Compensation

For their time and effort, participants will be compensated a total of \$100.00 for completion of the three assessment visits, including the 2-hour pre-treatment assessment and the 1 ½ hour post-treatment and 1-month follow-up assessments. The rates below are based on standard participant compensation in our ongoing VA clinical trials and were selected to enhance generalizability of feasibility and acceptability findings to our routine treatment-seeking Veterans, with due consideration of the need to minimize coercion.

### **Participant Compensation Schedule**

Completed Visit:	Amount to be Paid:
Pre-treatment Assessment Visit	\$25.00
1-Week Post-treatment Assessment Visit	\$25.00
1-Month Follow-up Assessment Visit	\$50.00
All Study Visits (3) Completed (Total):	\$100.00

## 10.0 Data Management

**Data Acquisition.** If (and only if) ultimately approved by the VA, we propose the use of VA Qualtrics, which is a secure, FedRAMP-authorized online data capture system that is widely used as a HIPPA-compliant web-based means to collect sensitive research data. Moreover, if approved, in addition to remotely collecting validated self-report questionnaire data from participants using this platform, we also request leveraging Qualtrics' functionality to integrate java script, which would enable us to directly capture audio and visual data from the participant's side from their webcam and microphone. This is an excellent alternative to our initially proposed procedures, which involve collecting streamed, then captured (i.e., on the clinician's side) footage. This is problematic due to significant temporal distortion and low sampling rate for screen-captured footage on currently deployed telehealth platforms approved by the VA (i.e., Teams, Webex, and VVC). As mentioned, the use of Qualtrics will be entirely contingent on obtaining full MUSC IRB and VA R&D approval for our proposed use. If ultimately not approved, we will continue to implement our procedures that involve capturing questionnaire data with hard copies, by mail.

**Data Preparation.** Pre-processing of data as the study progresses will allow for more expedient dissemination of study findings. As appropriate, pre-processing will follow standard best practices to ensure excellent data quality and security. Prior to analyses, data will be visually and statistically inspected for the presence of aberrant data points, which will be omitted prior to analyses.

**Analytical Plan.** Descriptive statistics will be reported for safety, feasibility, tolerability, and acceptability. Linear mixed-effects models will be used to characterize trajectories of change in symptoms and impairment, while controlling for potential confounders, such as baseline severity.

Following standard pre-processing steps, analyses will be conducted using generalized linear models, and will proceed in a bottom-up manner involving selection of the best fitting fixed and random growth terms, followed by adding predictors of interest. Factors (e.g., sex) will be dichotomously coded, whereas all continuous predictors will be scaled and centered as a function of baseline values to allow for meaningful interpretation of effects as indicative of reliable change.

Additionally, all models will control for baseline levels of the outcome to control for individual differences at pre-treatment in estimating effects. Model refinement will be guided by theory, evaluating standard fit statistics (e.g. Log Likelihood, AIC, BIC, etc.) and whether modeling assumptions are sufficiently met.

